## 2 INTRODUCTION

Asthma is one of the most common chronic diseases and is typically treated using pressurised metered dose inhalers (pMDIs). However, it is estimated that around 90% of people make errors

when using these, leading to poor symptom control and risks of serious asthma attacks as well as side-effects and medication overuse [1]. The Clip-Tone System (CTS) is a small device fitted to the top of the patients' inhaler which emits a specific sound with optimal inhaler use, that is detected by an accompanying mobile application (app) which provides real-time feedback to patients to improve their technique.

## Aims and objectives

This study aims to evaluate the impact of the Clip-Tone Buddy and app (Clip-Tone System; CTS) on improving the proficiency of inhaler use by patients and potential subsequent impact on their asthma control.

## **Methods**

[figure not shown]
This study involves a randomised controlled trial of the use of the CTS versus usual care in patients with asthma who are using pMDI devices. Participants will be primary care patients aged 16 years and over who are prescribed regular pMDI medication for asthma. After standard inhaler technique and asthma assessment, each of the participants will be randomised to either receive care as usual or to receive the CTS. All patients will be followed up remotely at 1 month, 3 months and 6 months following enrolment. At each follow-up, inhaler technique will be assessed and scored using the validated UK inhaler group checklist, asthma control questionnaire (ACQ5) completed and any relevant unscheduled GP or hospital visits recorded. To show a difference of 30% in the proportion of participants (63 per group), will be recruited allowing for a 20% dropout rate. Secondary objectives of this study are dedicated towards developing understanding of how patients perceive use of Clip-Tone System in a real-world setting. A health economic assessment of the data will also take place.

## **Dissemination and Impact**

The outputs of the research will be published in a peer reviewed journal and presented at national and international conferences. Results will be disseminated to participants. The planned research is intended to produce evidence to support the broad intended purpose of the CTS. It will allow for benefits to be understood and highlighted to users and potential customers.

The flow chart below summarises the study plan.

# 3 BACKGROUND

Asthma is one of the most prevalent chronic diseases – with 5.4million people receiving treatment in the UK [2] and 300million worldwide[3]. The mainstay of treatment is with inhaled medication. The advantage of administering medication by inhaler is that it is delivered directly to the airways, allowing rapid onset of action and minimising systemic side effects [4]. This medication can be highly effective, if taken correctly. However, it is estimated that around 90% of people make errors when using pressurised metered dose inhalers (pMDIs), the most common inhaler device used [5]. In addition to poor inhaler technique amongst patients, evidence shows healthcare professionals (HCPs) themselves make frequent errors and therefore are not always capable of demonstrating ideal technique to patients [6]. Using the correct technique can improve asthma symptoms, reduce risks of serious asthma attacks and reduce side effects and overuse of medication [1]. There is currently no objective method of assessing inhaler technique or an opportunity for patients to re-check their own technique. The proposed study aims to evaluate the use of a new inhaler technique self-management tool to assess the longer-term impact on proficiency of inhaler use and subsequent impact on disease control.

As asthma medication is predominantly given by inhaler, it is not surprising that inhaler technique errors have been linked with poor disease control [7]. Consequently, poor inhaler technique has been shown to lead to an increased risk of hospitalisation, A+E visits and oral steroid use [8]. In fact, inhaler technique review was one of a number of key recommendations in the National Review of Asthma Deaths [9]. As well as poor control, inadequate inhaler technique has resulted in increased side effects due to greater systemic absorption and patients requiring higher dose medications. Uncontrolled disease can impact patients' quality of life, and have indirect economic impacts through, for example, lost workdays affecting society as a whole [10]. The NHS long term plan (www.longtermplan.nhs.uk) lists respiratory care as a top priority, citing the fact admissions for respiratory disease have risen at 3 times the rate of admissions generally. Overall, asthma costs the UK health service at least £1.1billion each year, and around £666millon of this is spent on prescriptions [11], with similar impacts seen globally. By addressing this significant problem, and allowing patients to independently check their inhaler technique, some of these avoidable costs can be mitigated without compromising care.

## Existing literature supports the need for inhaler technique assessment.

NICE guidelines [12] on monitoring asthma control include frequent inhaler technique checks, at annual reviews, at every consultation following an asthma attack and whenever a new inhaler is prescribed. It also recommends that review opportunities are identified in community pharmacies. These checks involve subjective observation following demonstration by the HCP in the clinic setting and/or access to videos demonstrating optimal device use. However, despite these guidelines and resources, evidence shows that the situation has not changed in the last 40 years [13] and studies on inhaler technique have demonstrated that once trained and assessed as competent, patients' technique frequently wanes over time and training needs repeating regularly

[14]. In a recent document drawn up by the British Thoracic Society, review of inhaler technique was one of five elements highlighted as an action most likely to improve patient care [15]. However, many of these opportunities are lost due to lack of time and/or trained staff. Of note, many patients actively seek self-management opportunities, with a recent Asthma UK survey revealing that 93% of patients would welcome the use of apps to collect data to facilitate their interactions with their HCP [16].

Providing an effective method of reinforcing inhaler technique in the home setting on a regular basis, will help embed good habits. Reducing errors can improve clinical outcomes including disease control and fewer hospital admissions [1]. The use of the technology to be assessed here, Clip-Tone (Clement Clarke International, UK - collaborator) and the Clip-Tone Buddy app (Clin-e-cal Ltd, UK – lead applicant) is designed to provide exactly this support. Together these are known as the Clip-Tone System, CTS.

## Technology summary

Clip-Tone is a small device fitted to the top of the patients' inhaler. It is designed to emit a specific frequency of sound when the flow rate through the inhaler matches that of optimal technique. If inhalation speed fluctuates outside the ideal flow rate during the inhalation event, the whistle sound will stop or change. The Clip-Tone Buddy app identifies this specific sound frequency and provides real time feedback on inhalation length, and the timing of the sound of the actuation (canister press). When the inhalation has ceased an assessment of the users' technique will be displayed on the app, and tips to improve will be provided helping the patient master an effective technique.

The intended purpose of Clip-Tone Buddy is to guide inhaler technique and is a class I medical device accessory and tier 2 digital health technology, according to the digital evidence standards framework.

#### Supporting evidence for the use of the technology

Clin-e-cal's Sound Response technology is a software engine which identifies and responds to tones and sounds emitted by respiratory devices. To date the company has developed a successful app (Rafi-Tone) aimed at young children using inhalers with a spacer. This uses gamification techniques to engage and encourage the child [17]. Additionally, Clin-e-cal has developed a training app, Trainhaler Buddy, designed to help HCPs and patients develop appropriate inhalation flow and length. A study of 371 patients allocated to verbal counselling alone or verbal counselling with use of the Trainhaler Buddy found that patients trained using the app had a significant improvement in achieving the correct inhaler technique and also a significant early improvement in lung function and asthma control score, compared with the control group [18].

The Clip-Tone Buddy app has been built on this technology; developing a user-friendly app giving real-time inhaler technique feedback to optimise pMDI drug delivery. A preliminary study demonstrated that the deep and slow inhalation technique required when using a pMDI was improved in those using both the visual and audio feedback given with the Clip-Tone system

compared to verbal counselling alone [19]. Additionally, a small group of users have assessed the app for usability, informing the design and the development of the user interface and algorithm sensitivity.

The Clip-Tone System (CTS) can facilitate training when patients are first introduced to an inhaler and reinforce effective inhaler use whenever they use the device, embedding effective habits. The CTS is currently compatible with 90% of pressurised metered dose inhaler (pMDI) type inhalers prescribed in the UK (and pMDIs represent approximately 70% of UK inhaler prescriptions). The study described will examine the impact of the CTS on handling errors by assessing the inhaler technique score at 1, 3 and 6 months. As a secondary outcome, we will also examine the impact on asthma control. This will provide evidence that the CTS can address the long standing issue of inhaler technique which can be used in a health economic assessment to help drive uptake and adoption.

# **Funding**

This study has been awarded funding from an NIHR i4i Product Development Award. This is a collaborative application between the University of Manchester and Clin-e-cal Ltd (the Clip-Tone Buddy app developer). The grant reference is: 202884.

# 4 STUDY OBJECTIVES

**4.1** Primary Question/Objective:

The primary objective of the study is to answer the question: "Does use of the Clip-Tone System help people achieve and maintain effective inhaler technique for at least 6-months compared to those receiving care as usual?".

**4.2** Secondary Question/Objective:

Secondary questions that will be investigated with the data collected are:

"Do patients using the CTS have improved asthma control compared to those receiving care as usual?"

"Do patients using the CTS more frequently make fewer inhaler technique errors than those using it less frequently?"

## 5 STUDY DESIGN & PROTOCOL

## 5.1 Participants

The study will recruit 126 participants. These will be randomised into a care as usual group and an intervention group.

Participants will be over the age of 16 and will have a current asthma diagnosis. They will be currently prescribed one of the relevant inhalers (see section: 6.1).

## 5.2 Study Intervention and/or Procedures

The main aim of the study is:

To establish whether the use of the Clip-Tone System (CTS) improves and maintain inhaler technique in asthmatic patients (> 16 years) over a 6-month period compared with those receiving "usual care" alone.

Other aims include:

To assess the use of the CTS in asthmatic patients (> 16 years) and its effects on asthma control and

unscheduled clinical visits over a period of 6-months

To develop understanding of how patients use CTS in a real-world setting.

To develop understanding of what frequency of use of CTS is desirable.

## The technology: Clip-Tone System

The technology consists of two parts:

1) Clip-Tone - a small plastic retrofit device available in two variants (developed and manufactured by commercial partner Clement Clarke International; both CE marked, Class I medical devices available on prescription from May 2021) (See Figure A, Appendix 1)

a) Clip-Tone E fits GSK manufactured Evohalers (Ventolin, Flixotide, Seretide brands)

b) Clip-Tone F fits Chiesi manufactured inhalers (Fostair, Trimbow, Clenil brands),

2) Clip-Tone Buddy app - class I medical device accessory (CE marked), available on Apple and Google app stores.

Both parts of the system are independently protected by patents (granted and pending) - a collaboration agreement is in place clearly delineating background and foreground IP ownership.

### Study design

General points:

Although the CTS is currently available (Clip-Tone on prescription and Clip-Tone Buddy app available to purchase on App store) we currently do not know how effective it is in improving and maintaining inhaler technique in patients with asthma. If this data were available, health care professionals would know whether to advise patients to use it. Potentially this is a low-cost solution to a large problem within the asthma community.

In order to gain this evidence, it is important to compare the use of the CTS with "usual care". Some patients will already have good inhaler technique and have adequate education on how to use their inhaler – we do not want to interfere with this and so all patients in the study will continue to see their HCPs as and when they are invited to do so or if the need arises during the study. We will simply ask patients to report what input they have had when we follow them up at each visit. We plan to randomly assign half the participants to the CTS, along with their "usual care" and half to continue with their "usual care" only.

During the Covid pandemic patients have become accustomed to having many of their health consultations performed remotely by video or telephone consultation. The public in general have become used to talking with friends, family, colleagues and having work meetings via Zoom, Microsoft Teams or Facetime. Virtual consultations generally are time saving with no travel time

for participants and easier to fit into our everyday lives. Participants who enter into this study need to have the availability of a mobile smartphone or a tablet in order that they can participate. For these reasons we have planned to carry out the study using virtual consultations. We appreciate that the nature of the study will exclude some members of the public but with smartphone ownership at >90% of all UK under 65-year-olds (OFCOM data 2020) the numbers excluded in this study will be small.

We will reassess recruitment within the first 4-8 weeks of the study and if it is felt participants are being excluded because they want to have face-to-face consultations rather than virtual ones, we will source rooms to see participants and submit an amendment to the protocol and ethics committee.

In developing the project plan we have collaborated with Greater Manchester Clinical Research Network (GMCRN) Study Support Services Lead, and Speciality Lead for Primary Care, [name], who have contributed to the study design and advised on recruitment strategy. We have had input from patients and public through the GMCRN Research for Futures group and have enlisted a patient to be part of our trial management group to help throughout the study. We have also had advice from North West Research Design Service on study design and sample size.

## Methods:

We will carry out a randomised controlled study comparing inhaler technique in those using Clip-Tone System (CTS) with standard care (the "usual care" group) over a 6 month period. Through the GMCRN, primary care practices will be asked to search their databases and identify patients meeting the inclusion criteria. Greater Manchester covers a wide area with diverse populations, including geographical (urban and rural), socioeconomic, ethnicities and ages. Using text messaging services patients will be informed about this study and be directed to an online recruitment portal which will consist of a short questionnaire to include/exclude potential participants. This questionnaire will also include questions related to equality and diversity to allow assessment of whether the opportunity to participate is reaching a broad range of eligible patients. It will include access to the detailed patient information sheet (PIS). If the patient is identified as potentially eligible the researcher will arrange an appointment. In addition, we will advertise the study in health care settings, e.g., GP practices and pharmacies and potential recruits will be able to access the website or call the research team directly to obtain verbal study information, complete the eligibility questionnaire and receive the PIS.

We hope to have kept the inclusion criteria as broad as possible in order to reflect real world testing of the CTS as much as possible.

#### Eligibility Criteria:

- 1) Over the age of 16
- 2) Self-reported asthma diagnosis and currently receiving treatment
- 3) Must be regularly prescribed one of the following brands of inhaler Fostair, Seretide, Flixotide, Clenil, Trimbow (those that fit the Clip-Tone E or F) and have been using it for at least 1-month prior to enrolment.
- 4) Access to a smartphone or tablet device and willingness to use it to regularly assess inhaler technique for the study duration.

#### Exclusion criteria:

1) Using a spacer to assist with using their inhaler.

- 2) Prescribed oral steroids for asthma in the preceding 1-month
- 3) Medication is not self-administered
- 4) Treatment for acute asthma in an ICU within the previous 3 years
- 5) Insufficient understanding of spoken and/or written English (as judged by the researcher).

Potential recruits will attend a baseline visit where formal content to participate will be taken and eligibility criteria checked. Initial inhaler technique will be assessed using a formal inhaler technique score. Asthma control questionnaire will be completed (a validated asthma questionnaire to detect level of asthma symptom control). Some baseline questions will be asked about their asthma e.g. medication, exacerbations, HCP involved. We plan to randomise 126 participants, half to CTS and half to Usual care.

Those allocated to the CTS group will have the Clip-Tone posted to them along with a voucher code for the Clip-Tone Buddy App and a short virtual visit will be arranged the following week to ensure the participant knows how to use the device and the features of the app.

Participants will all attend 3 further follow-up visits in 1, 3 and 6 months. For the "usual care" group these visit dates will be calculated from the baseline appointment, and for the CTS group these will be calculated from the training visit. The difference in these calculations is to allow for any delay in the participant commencing use of the CTS, to ensure that 6 months of active intervention usage are accurately recorded.

At each follow up visit inhaler technique will be assessed using the formal inhaler technique score. Asthma control questionnaire will be completed and a few questions will be asked about asthma health care utilisation since the previous visit. Those in the CTS group will be asked to send a screen shot of the app use and to give some feedback on useability, frequency of use, barriers to use and suggested improvements.

At all study visit all patients will also have their inhaler technique video recorded. For the Baseline (V1) and the final visit (V4) these recordings will be scored blindly (not knowing which group they are in) by an independent assessor. This is to reduce the element of bias in the study, as the participant and researcher carrying out the visit will know if they are using the CTS. Participants can opt out of this should they wish. At the other two visits, at one month (V2) and three months (V3) the inhaler technique will also be recorded but only to allow for the researcher to review the technique post visit, to ensure correct assessment results. These recordings would be destroyed directly after this is completed and not sent for blind assessment.

We hope to recruit patients over a 9-12 month period from June 2021. Patients will be in the study for 6 months.

Participants will be offered a small payment for each visit they attend (£15), as a thank you and recognition of any inconvenience caused.

At the end of the study the CTS group can keep using the app should the wish and the "usual care" group can be sent one to use should they wish to try it out.

Each participant will be enrolled in the study for approximately 6-months. Participants will selfrefer into the study, via short online questionnaire. They will be asked a few basic questions to check eligibility (see section: 6.3). Following initial eligibility check, a patient information sheet will be sent to the patients and contact with the patient will be made. If the patient is willing a

baseline appointment will be made. At this baseline appointment consent will be obtained. Following consent some demographic details and asthma history will be obtained and the participant will be randomised.

If they are allocated to the intervention group, a Clip-Tone device will be sent to them, along with details of the app and how to upload it and a follow up training session will be made to ensure the participant can use the CTS.

After the baseline visit all participants will be asked to attend three further follow-up visits, 1-month, 3-months and 6-months later.

At all of the visits participants will be asked to demonstrate their inhaler technique which will be observed and scored according to the inhaler technique checklist. This demonstration will also be video recorded, at baseline (V1) and final visit (V4) this is to enable a blind assessment of their technique by an independent observer and at month 1 (V2) and month 3 (V3) only for researcher assessment, prior to immediate destruction. The table below summarises the appointments and what will happen to participants during the study.

	Pre-screening (pre-consent)	Baseline Appointment: T=0	Training for intervention arm: T=7days (+/-7)	Visit 1: T=28 days (+/-7 days)	Visit 2: T=90 days (+/- 14 days)	Visit 3: T=182 days (+/- 28 days)
Database searches	Х					
Participant initiated eligibility screen	х					
Informed Consent		Х				
Demographics		Х				
Relevant clinical history		Х		х	х	x
Recorded Inhaler technique (for blinded assessment)		Х				x
Recorded Inhaler technique assessment		Х		Х	Х	х

(by					
researcher)					
A ath we a					
Asthma					
Control	Х		Х	Х	Х
Questionnaire					
Dandamiaatian	V				
Randomisation	Х				
Training on					
use of		Х			
intervention					

# 5.3 End of study

A participant is considered to have completed the study if they have completed the baseline assessment, the intervention guidance appointment (if randomised to the intervention group) and the follow up appointments at 1, 3 and 6 months. As a minimum at the baseline and all follow up appointments, inhaler technique assessment and ACQs will be completed. Participants may opt out of the video recording of inhaler use if desired (these blinded assessments are intended to verify the veracity of the researcher assessment who cannot be blinded due to the nature of the intervention).

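### The protocol does not make the blinded video score the analysed outcome, and does not protect the blinding of the 6-month video

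*Protocol*

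**What the plan says.** Who scores. Protocol Section 5.2 states: "At all of the visits participants will be asked to demonstrate their inhaler technique which will be observed and scored according to the inhaler technique"; the instrument is a checklist. The schedule table in that section gives this task to the researcher at baseline and at all three follow-ups. The same section explains why a second rating is wanted, "as the participant and researcher carrying out the visit will know if they are using the CTS".

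The blinded rating. For the baseline and final visits, "these recordings will be scored blindly (not knowing which group they are in) by an independent assessor". The 1- and 3-month recordings are seen only by the researcher and then destroyed.

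What the blinded rating is for. There are two statements:
- Section 5.2: "This is to reduce the element of bias in the study".
- Section 5.3: "these blinded assessments are intended to verify the veracity of the researcher assessment who cannot be blinded due to the nature of the intervention". Section 5.3 also makes the technique assessment part of the minimum data at every visit but leaves the film optional: "Participants may opt out of the video recording of inhaler use if desired".

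The analysis. Section 10.1 compares the arms on improvement in technique score from baseline to 6 months, and on the score at each follow-up. It does not name the rater, mention the blinded score or say what happens if the two ratings disagree.

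The device. Section 3 (Technology summary) describes a part fitted to the top of the inhaler: "It is designed to emit a specific frequency of sound when the flow rate through the inhaler matches that of optimal technique". The protocol does not say whether it is on the inhaler during the filmed demonstration.

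**The concern.** The outcome is a checklist completed by an observer, so knowledge of the arm can influence the score. The trial already plans the remedy, an independent blinded rating at the two times that the main comparison needs. Section 5.3 nevertheless gives that rating the role of a check on the unblinded one, and Section 10.1 does not assign it to the analysis. A blinded rating reduces bias in the result only if it is the rating analysed, or if a rule says what follows from disagreement. The protocol provides neither.

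The blinding itself is also exposed. If a CTS participant demonstrates with the Clip-Tone in place at 6 months, the assessor can see and hear which arm it is.

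At stake is whether a between-arm difference reflects technique or the rater's expectation. Section 10.1 also compares the proportion reaching the maximum score of 10. There, a single lenient step turns a 9 into a correct technique.

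**Working it through.** **1. Inputs.** Section 10.2 gives final means of 9.5 and 8.9 (difference 0.6), SD 1 in each arm, significance level 0.05, a minimum of 88 participants, and 126 recruited to allow for 30% drop-out. It states neither sidedness nor power; I assume two-sided and 80%.

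**2. The plan's own figure.** n per arm = 2 × (1.96 + 0.842)² × 1² / 0.6² = 43.6, rounded up to 44, so 88 in total. Then 88 / 0.70 = 125.7, so 126. Both figures reproduce, and this point does not depend on an error in them.

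**3. Does rater bias cancel in change from baseline?** Section 6.4 randomises after baseline data are gathered, so the baseline score cannot depend on the arm. If the 6-month CTS score is raised by b on average:

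expected difference in change = true effect + b − 0 = true effect + b.

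The bias passes through undiminished.

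**4. Size of b (assumption).** The documents give no leniency rate. If one extra step is passed in 20% or 30% of CTS participants, b = 0.2 or 0.3 points. As a share of 0.6 that is 33% or 50%.

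**5. False-positive rate with no true effect.** Take SE = √(2/n) with SD 1, a normal approximation, and the bias as a shift that leaves the SD unchanged. Then

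P(reject) = Φ(b/SE − 1.96) + Φ(−b/SE − 1.96).

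| n per arm | SE | b = 0.1 | b = 0.2 | b = 0.3 |
|---|---|---|---|---|
| 44 | 0.213 | 7.6% | 15.5% | 29.1% |
| 63 | 0.178 | 8.7% | 20.2% | 39.1% |

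For example, with n = 44 and b = 0.2, b/SE = 0.938, and Φ(−1.022) + Φ(−2.898) = 0.153 + 0.002 = 0.155. More participants make this worse, because a fixed bias is then tested with a smaller SE.

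**6. Power if the blinded score is analysed and video opt-outs are missing.** The opt-out rate is not given. Power = Φ(0.6/SE − 1.96) for a true difference of 0.6.

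| Participants with 6-month follow-up | 0% opt-out | 10% | 20% |
|---|---|---|---|
| 88 | 80.4% | 76.1% | 71.1% |
| 126 | 92.0% | 89.2% | 85.4% |

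**7. Which video can show the arm?** Baseline is filmed before allocation, and the Clip-Tone is posted afterwards (Section 5.2). The trial device can therefore reveal the arm only in the 6-month video.

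**The case against.** The best defence is that Section 10.1 names no rater at all. It no more selects the researcher's score than the blinded one. Section 5.2 gives the blinded scoring a bias-reducing purpose and schedules it at baseline and 6 months, and the choice between two planned ratings is often left to an analysis plan, which is not at hand. This stands in part. A reader might infer that the researcher's score is definitely the analysed one; the text does not say so. But the protocol is not merely silent. Section 5.3 fixes the blinded score as a verification, which conflicts with Section 5.2.

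Other stronger readings are also not supported:
- *Leniency could create or double the planned effect.* At one step each, adding 0.6 points would take about 60% of CTS participants (0.6 / 1), not a minority. With a maximum of 10 and a planned CTS mean of 9.5, and if both are on the same scale, average headroom is only 0.5. The assumed rates support adding a third to a half.
- *The videos reveal the arm.* This is an inference from the device description and the lack of a masking step. Section 5.2 does commit to an assessor unaware of the group.
- *The visit labels put the key recording at risk.* In the text V3 is the 3-month visit, whose film is destroyed, while the table has "Visit 3: T=182 days (+/- 28 days"). But the text gives the months beside the labels, and the table marks blinded recording at baseline and 182 days. This is a clerical mismatch.

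**Conclusion.** The point holds in this form: the protocol describes the blinded score's role in two ways, does not make it the analysed outcome, and leaves the masking of the 6-month video unprotected. The 1- and 3-month comparisons can rest only on the unblinded researcher, because those films are destroyed.

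If the researcher's 6-month score is analysed, a bias of 0.2-0.3 points is one third to one half of the planned difference. It takes the false-positive rate from 5% to about 15-29% at 44 per arm and about 20-39% at 63 per arm. These figures depend on an assumed leniency rate of 20-30%, on SD 1 for the analysed quantity (Section 10.2 gives it for final scores) and on a two-sided 0.05 test. They show how sensitive the result is; they do not estimate the bias that will occur.

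**What to change.** 1. **Section 10.1:** name the independent blinded 6-month score, adjusted for the blinded baseline score, as the primary analysed outcome. Keep the researcher's score as a supportive analysis.
2. **Section 5.3:** reword the purpose of the blinded scoring to agree with Section 5.2.
3. **Video opt-outs:** treat them as missing in the primary analysis and cover them in a sensitivity analysis using the researcher's score. Filling them with the researcher's score in the primary analysis would bring unblinded ratings back in. Report opt-outs, and blinded-minus-researcher differences, by arm.
4. **Section 5.2:** require the 6-month filmed demonstration in both arms to be done without the Clip-Tone and app, or mask picture and sound before scoring. The first option measures technique on the bare inhaler and the second may measure technique with the device, so the protocol should say which it means. No such step is needed at baseline.
5. **1- and 3-month comparisons:** label them unblinded and secondary.
6. **Housekeeping:** align the visit numbers in the text and table.

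Cost: blinded scoring is already planned, so this is mainly wording plus a line in the visit script or a masking step. The real price is power lost to opt-outs. With 88 completers it falls from about 80% to about 76% at 10% opt-out and 71% at 20% (opt-out rates assumed).
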